4.5.1.3 Dose Preparation Steps

The final delivery volume and concentration for each dose level and the syringe sizes to be used for preparation are described in Table 4.5.1.3-1.

Table 4.5.1.3-1 MEDI0382 and Placebo Dose Preparation

Dose Level	Formulation Stock Concentration (mg/mL)	Volume of Injection (mL)	Number of Units ^b	Syringe Size
50 µg or placebo	0.2	0.25 ^a	NA	1 mL
100 µg or placebo	2.0	0.05	5	0.3 mL
200 µg or placebo	2.0	0.1	10	0.3 mL
300 µg or placebo	2.0	0.15	15	0.3 mL

^a For the 50 µg dose, the stock concentration will be achieved by dilution in the clinic.

^b The 0.3-mL syringe is marked in “units” where each unit = 0.01 mL and 0.15 mL = 15 units.

No incompatibilities between MEDI0382 and plastics passing compatibility tests (ie, polyolefin or polyvinylchloride syringes) have been observed.

1. Investigational product is supplied in 3-mL glass vials at a nominal concentration of 2 mg/mL.
2. Determine from [Table 4.5.1.3-1](#) the correct dose level and injection volume.
3. For doses of 50 ug a 10-fold diluted stock concentration of 0.2 mg/mL will be prepared by site staff at the clinical unit, prior to administration.
4. To make a 10-fold diluted MEDI0382, it is recommended to take 0.1 mL of MEDI0382 investigational product using a needle and 1-mL syringe, add it into a sterile empty vial, followed by addition of 0.9 mL of diluent into the same vial using a needle and 1-mL syringe. The vial should be mixed by swirling gently to make a homogenous final admixture. Do not shake. The diluted dose should be administered using a 1-mL syringe.

The 100- μ g, 200- μ g, and 300- μ g doses do not require a dilution step and should be administered using a 0.3-mL syringe. For the 50 μ g dose, dilution steps will need to be carried out by site staff at the clinical unit.

At-home Dose Preparation Steps

No dilution steps for preparation of investigational product will be performed by the subject at home; all dilution steps will be performed at the study site. The 50- μ g dose is always administered in the clinic.

4.5.1.4 Treatment Administration

If diluent is required: investigational product should be removed from the refrigerator and kept at room temperature for at least 30 minutes and a maximum of 2 hours for temperature equilibration. If no diluent is required, 15 minutes is recommended for temperature equilibration.

In-clinic Treatment Administration

The first day of dosing is considered Day 1. On the day of each dose, investigational product will be administered according to the schedule of procedures. On study days where fasting is required for an additional assessment, the investigational product should be taken 2.5 hours prior to any MMTT [REDACTED]. Investigational product will be administered by SC injection in the lower abdomen utilising either a 0.3-mL or a 1-mL insulin syringe according to the dose level. Refer to the Investigational product manual.

At-home Treatment Administration

Investigational product should be removed from the refrigerator for at least 15 minutes for temperature equilibration.

A once-daily dose is to be self-administered by SC injection using a 0.3-mL insulin syringe as soon as practicable upon waking each morning prior to breakfast. The investigational product is packaged in a carton with sufficient vial kits. Each vial contains 1 mL of liquid product with adequate overfill. The carton must be stored in the refrigerator. Refer to the home dosing instructions.

If a dose of MEDI0382 or placebo is missed, subjects should take the dose as soon as it is remembered unless it is almost time for the next dose, in which case subjects should skip the missed dose and take the study drug at the next regularly scheduled time.

4.5.1.5 Monitoring of Dose Administration

As with any exogenous peptide delivered subcutaneously, allergic reactions to dose administration are possible. In prior experience with MEDI0382 there has been one injection site reaction and no anaphylactoid reactions. During visits to the clinical unit, the site of administration will be checked for signs of injection site reaction as required (Section 4.3.2.2).

4.5.2 Additional Study Medications

No other study medications are specified for use in this clinical protocol.

4.5.3 Labeling

Labels for the investigational product will be prepared in accordance with Good Manufacturing Practice (GMP) and local regulatory guidelines. The label will fulfill GMP Annex 13 requirements for labeling. Label text will be translated into local languages, as required.

4.5.4 Storage

Store investigational product at the clinical site at 2°C to 8°C. Investigational product taken home by the subject must be stored in a refrigerator and must not exceed 25°C.

4.5.5 Treatment Compliance

Investigational product is administered by study site personnel, who will monitor compliance.

4.5.6 Accountability

The investigator's or site's designated investigational product manager is required to maintain accurate investigational product accountability records. Upon completion of the study, copies of investigational product accountability records will be returned to MedImmune. All unused investigational product will be returned to a MedImmune-authorized depot or disposed of upon authorization by MedImmune.

4.6 Treatment Assignment and Blinding

4.6.1 Methods for Assigning Treatment Groups

An interactive web response system (IWRS) will be used for randomisation to a treatment group and assignment of blinded investigational product kit numbers. A subject is considered randomised into the study when the investigator notifies the IWRS that the subject meets eligibility criteria and the IWRS provides the assignment of blinded investigational product kit numbers to the subject.

4.6.1.1 Cohort 1

Subjects will be randomised using a ratio of 2:1 to one of 2 treatment arms to receive either MEDI0382 titrated up to 300 µg or placebo. Sufficient subjects will be invited to participate

in the study such that a maximum of 26 will complete dosing in the active arm and 13 will complete dosing in the placebo arm.

4.6.1.2 Cohort 2

Subjects will be randomised using a ratio of 3:1 to receive either MEDI0382 titrated up to 300 µg or placebo respectively. Sufficient subjects will be invited to participate in the study such that a maximum of 18 will complete dosing in the active arm and 6 will complete dosing in the placebo arm.

4.6.2 Methods for Ensuring Blinding

This is a double-blind study in which MEDI0382 and placebo are identically labeled and indistinguishable in appearance. As such, neither the subject nor any of the investigator or sponsor staff who are involved in the treatment or clinical evaluation of the subjects will be aware of the treatment received (ICH E9). (See Section 4.6.3.2 for unblinding related to the interim analysis.) In the event that treatment allocation for a subject becomes known to the investigator or other study staff involved in the management of study subjects, the sponsor must be notified *immediately*.

4.6.3 Methods for Unblinding

4.6.3.1 Unblinding in the Event of a Medical Emergency

In the event of a medical emergency, the investigator may unblind an individual subject's investigational product allocation. Instructions for unblinding an individual subject's investigational product allocation are contained in the IXRS manual. In general, unblinding should only occur if management of the medical emergency would be different based on the subject having received investigational product. In the majority of cases, the management of a medical emergency would be the same whether or not investigational product was received by the subject. If this was the case, the investigational product allocation should not be unblinded.

MedImmune retains the right to unblind the treatment allocation for SAEs that are unexpected and are suspected to be causally related to an investigational product and that potentially require expedited reporting to regulatory authorities.

4.6.3.2 Unblinding for Interim Analysis Purposes

An interim analysis is planned for this study after the last subject has received their last dose as described in Section 4.8.6. Only the study team pharmacokineticist will be unblinded and only descriptive PK analyses will be performed. The unblinded pharmacokineticist will stop

day-to-day work on the study and other pre-selected personnel will take over these roles for the remainder of the trial.

4.7 Restrictions During the Study and Concomitant Treatment(s)

The investigator must be informed as soon as possible about any medication taken from the time of screening until the end of the study (final study visit). Any concomitant medication(s), including herbal preparations, taken during the study will be recorded in the eCRF.

4.7.1 Permitted Concomitant Medications

Investigators may prescribe concomitant medications or treatments deemed necessary to provide adequate supportive care except for those medications identified as “excluded” as listed in Section 4.7.2. Specifically, subjects should receive full supportive care during the study, including transfusions of blood and blood products, and treatment with antibiotics, antiemetics, anti-diarrhoeals, and analgesics, and other care as deemed appropriate, and in accordance with their institutional guidelines.

4.7.2 Prohibited Concomitant Medications

Other than the medications described above, use of concomitant medications including over-the-counter medications, herbal supplements, vitamin, etc at the times specified in the list below is not permitted. Subjects must be instructed not to take any medications, including over-the-counter products, without first consulting with the investigator.

Subjects should not be initiated on any new medications to control blood glucose levels during the dosing and follow-up period unless it is deemed necessary by the investigator for safety and following discussion with the medical monitor. Refer to Section 3.1.4.3 for further details.

- Concurrent or previous use of a GLP-1 analogue containing preparation within the last 30 days or 5 half-lives of the drug, whichever is longest, prior to the start of screening (Visit 1)
- Concurrent use of any herbal preparations or medicinal products licensed for control of body weight or appetite and within 1 week prior to the start of the study (Visit 2)
- Concurrent or previous use of drugs approved for weight loss (eg, orlistat, bupropion-naltrexone, phentermine-topiramate, phentermine, lorcaserin) and within the last 30 days or 5 half-lives of the drug, whichever is longest, prior to the start of the study (Visit 2)

- Concurrent use of aspirin (acetylsalicylic acid) at a dose greater than 150 mg once daily and within the last 72 hours prior to the start of the study (Visit 2)
- Concurrent use of paracetamol (acetaminophen) at a total daily dose greater than 3000 mg once daily and within the last 72 hours prior to the start of the study (Visit 2)
- Concurrent use of ascorbic acid (vitamin C) at a total daily dose of > 1000 mg and within the last 72 hours prior to the start of the study (Visit 2)
- Concurrent use of opiates, domperidone, metoclopramide, or other drugs [REDACTED] within 2 weeks prior to the start of the study (Visit 2) [REDACTED]
- Concurrent use of medications (other than metformin) for control of blood glucose within 4 weeks prior to the start of the study (Visit 2) unless it is deemed necessary by the investigator for safety reasons.

4.8 Statistical Evaluation

4.8.1 General Considerations

Tabular summaries will be presented by treatment group. Categorical data will be summarised by the number and percentage of subjects in each category. Continuous variables will be summarised by descriptive statistics. Additional details of statistical analyses will be described in the statistical analysis plan.

4.8.1.1 Analysis Populations

Efficacy Analysis Set

The Intent-to-treat (ITT) population includes all subjects who receive at least one dose of any investigational product and will be analysed according to their randomised treatment group.

Safety Analysis Set

The As-treated population includes all subjects who receive at least one dose of any investigational product and will be analysed according to the treatment they actually receive.

PK Analysis Set

The PK population includes all subjects who received at least one dose of investigational product and had at least one PK sample taken that is above the lower limit of quantitation.

[REDACTED]

4.8.3 Efficacy

4.8.3.1 Primary Efficacy Analysis

The efficacy analysis will be based on the ITT population. The coprimary efficacy endpoints of percentage glucose AUC change and percentage weight change from baseline to 49 days (Section 2.1) will be compared between MEDI0382 and placebo arms, using an analysis of covariance (ANCOVA) model, adjusting for treatment and measurement at baseline.

4.8.3.2 Secondary Efficacy Analyses

For analyses of the secondary endpoints (Section 2.2), an ANCOVA model similar to the primary efficacy analysis will be used for continuous endpoints. For proportion-related endpoints, a logistic regression model will be used with fixed effects of treatment and baseline measurement. For the secondary endpoint evaluating glucose AUC reduction at the 50 µg dose level, only glucose readings taken at 0, 15, 30, 45, 60, 90, 120, 180, and 240 minutes will be used in this analysis.

4.8.3.3 Exploratory Analyses

For analyses of the exploratory endpoints (Section 2.3), an ANCOVA model similar to the primary efficacy analysis will be used for continuous endpoints. For proportion-related endpoints, a logistic regression model will be used with fixed effects of treatment and baseline measurement.

4.8.4 Safety

AEs and SAEs will be coded by the most updated version of Medical Dictionary for Regulatory Activities (MedDRA), and the type, incidence, severity, and relationship to study investigational product will be summarised by MedDRA System Organ Class and Preferred

Term and by treatment. AEs leading to discontinuation, AEs leading to death, and deaths will also be summarised and will be marked in the listings or will be in a separate listing. Specific AEs will be counted once for each subject for calculating percentages. In addition, if the same AE occurs multiple times within a particular subject, the highest severity and level of relationship observed will be reported. Subject-level data listings of all AEs will be presented.

4.8.4.1 Analysis of Clinical Laboratory Parameters

Other safety data, such as vital signs, clinical laboratory data, ECG, and physical examination findings, will be descriptively summarised at each time point by treatment. Mean ambulatory BP and heart rate measurements recorded over 24 hours at different time points will be analysed using an ANCOVA model, adjusting for treatment and measurement at baseline. ADA incidence rate and titre will be tabulated for each treatment.

4.8.5 Analysis of Immunogenicity/Pharmacokinetics

Pharmacokinetic parameters such as MEDI0382 C_{max} , T_{max} , AUC, and $T_{1/2}$ will be estimated if data allow, from plasma concentration time data for MEDI0382 at the 50 and 300 μg dose level separately.

Descriptive statistics will be generated for PK parameters for the MEDI0382 group in each cohort. Subjects who have at least one measurable concentration time point of investigational product will be used for this analysis.

The incidence and impact of ADA to MEDI0382 will be evaluated. The number and percentage of subjects with confirmed positive serum antibodies to MEDI0382 will be reported by dose level. Data on titres and cross-reactivity to GLP-1 and glucagon (where applicable) will be listed. If warranted by the data, the association of ADA positive with observed PK data may be explored.

4.8.6 Interim Analysis

An interim database lock for analysis of PK data only will be performed just after last subject last dose. Only the study team pharmacokineticist will be unblinded at this stage and will use the data to perform descriptive PK analyses. All other analyses will take place after final database lock.

5 ASSESSMENT OF SAFETY

5.1 Definition of Adverse Events

The ICH Guideline for GCP E6(R1) defines an AE as:

Any untoward medical occurrence in a patient or clinical investigation subject administered a pharmaceutical product and which does not necessarily have a causal relationship with this treatment. An AE can therefore be any unfavorable and unintended sign (including an abnormal laboratory finding), symptom, or disease temporally associated with the use of a medicinal product, whether or not considered related to the medicinal product.

An AE includes but is not limited to any clinically significant worsening of a subject's pre-existing condition. The term disease progression should not be reported as an AE or SAE; however, medically significant individual events and/or laboratory abnormalities associated with disease progression (see definition of disease progression below) that fulfill the AE or SAE definition should be reported. An abnormal laboratory finding (including ECG finding) that requires medical intervention by the investigator, or a finding judged by the investigator as medically significant should be reported as an AE. If clinical sequelae are associated with a laboratory abnormality, the diagnosis or medical condition should be reported (eg, renal failure, hematuria) not the laboratory abnormality (eg, elevated creatinine, urine red blood cell count increased). Abnormal laboratory values that are not, in the investigator's opinion, medically significant and do not require intervention should not be reported as AEs.

Adverse events may be treatment-emergent (ie, occurring after initial receipt of investigational product) or non-treatment emergent. A non-treatment-emergent AE is any new sign or symptom, disease, or other untoward medical event that begins after written informed consent has been obtained but before the subject has received investigational product.

Elective treatment or surgery or preplanned treatment or surgery (that was scheduled prior to the subject being enrolled into the study) for a documented pre-existing condition that did not worsen from baseline is not considered an AE (serious or nonserious). An untoward medical event occurring during the prescheduled elective procedure or routinely scheduled treatment should be recorded as an AE or SAE.

5.2 Definition of Serious Adverse Events

An SAE is any AE that:

- Results in death
- Is immediately life-threatening
- Requires inpatient hospitalisation or prolongation of existing hospitalisation
- Results in persistent or significant disability/incapacity
- Is a congenital anomaly/birth defect in offspring of the subject
- Is an important medical event that may jeopardise the subject or may require medical intervention to prevent one of the outcomes listed above

Medical or scientific judgment should be exercised in deciding whether expedited reporting is appropriate in this situation. Examples of medically important events are intensive treatment in an emergency room or at home for allergic bronchospasm, blood dyscrasias, or convulsions that do not result in hospitalisations; or development of drug dependency or drug abuse.

5.3 Definition of Adverse Events of Special Interest

An adverse event of special interest (AESI) is one of scientific and medical interest specific to understanding of the investigational product and may require close monitoring and collecting additional information by the investigator and reporting to the sponsor. An AESI may be serious or nonserious. The rapid reporting of AESIs allows ongoing surveillance of these events in order to characterise and understand them in association with the use of this investigational product.

All AESIs should be recorded in the eCRF within 24 hours. In addition, AESIs that are also SAEs should be reported to the appropriate sponsor representative within 24 hours. Instructions to the site on how to record (in the eCRF) and report an AESI are provided in Section 5.3.1 and Section 10.5, respectively. The AESIs for this study are defined below.

5.3.1 Hepatic Function Abnormalities

Refer to Section 5.6.2 and Section 10.5 for the definition and follow-up for liver abnormalities. There are no other AESIs in this study.

5.4 Recording of Adverse Events

Adverse events will be recorded on the eCRF using a recognised medical term or diagnosis that accurately reflects the event. Adverse events will be assessed by the investigator for severity, relationship to the investigational product, possible aetiologies, and whether the event meets criteria of an SAE and therefore requires immediate notification to the sponsor

(Section 5.5). See Section 5.2 for the definition of SAEs and Section 10.3 for guidelines for assessment of severity and relationship. If an AE evolves into a condition that meets the regulatory definition of “serious,” it will be reported in the eCRF.

5.4.1 Time Period for Collection of Adverse Events

All AEs will be collected from the time of admission to the clinical unit (Day -2 for Cohort 1 and Day -2 [REDACTED] for Cohort 2) throughout the treatment period and including the follow-up period (7 to 14 days after the last dose of investigational product; Visit 10 for Cohort 1 [Table 4.2.2-1] and Visit 8 [Table 4.2.2-2] for Cohort 2). Additionally, all SAEs will be collected from time of signature of informed consent throughout the treatment period and including the follow-up period as described above.

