2.2 Secondary Objectives and Associated Endpoints

Table 2.2-1 Secondary Objectives and Associated Endpoints

Type	Objective	Endpoint
Efficacy	To assess the effects of MEDI0382 titrated up to a dose level of 300 µg on additional measures of glucose control and body weight versus placebo after 49 days of treatment (Cohort 1 only)	
 Change in HbA1c from baseline (Day - 1) to the end of 49 days of treatment Change in fasting plasma glucose (Day -1) from baseline to the end of 49 days of treatment Change in body weight (kg) from baseline (Day 1) to the end of 49 days of treatment Proportion of subjects achieving > 5% body weight loss from baseline (Day 1) after 49 days of treatment
Safety	To characterise the safety profile and tolerability of MEDI0382 titrated up to a dose level of 300 µg during dosing and follow-up (Cohorts 1 and 2)	Measures of safety and tolerability (24-hour heart rate and blood pressure, other vital signs, ECG, laboratory test results, and AEs)
PK, Immunogenicity	To characterise the PK profile and immunogenicity of 50 and 300µg of MEDI0382 (Cohorts 1 and 2)	
 PK endpoints for 50 µg MEDI0382 after 1, 7, and 14 days of treatment and 300 µg MEDI0382 after 1 and 28 days of treatment; AUC over a dosing duration, C_{max}, T_{max}, T_{1/2}, trough plasma concentration (C_{trough}), and accumulation ratio (C_{min} [R₀]) Development of anti-drug antibodies and titre (if confirmed positive)
Efficacy	To characterise the effect of 50 µg of MEDI0382 on glucose lowering versus placebo after 7 days (Cohorts 1 and 2)	Percentage change in glucose AUC as measured by a standardised MMTT from baseline (Day -1) to the end of 7 days of treatment

Table 2.2-1 Secondary Objectives and Associated Endpoints

Type	Objective	Endpoint
------	-----------	----------

AE = adverse event; AUC = area under the concentration-time curve; C_{max} = maximum observed concentration; C_{min} [R_0] = accumulation ratio; C_{trough} = trough plasma concentration;
ECG = electrocardiogram; HbA1c = glycated haemoglobin; MMTT = mixed-meal tolerance test;
PK = pharmacokinetic; $T_{1/2}$ = terminal half-life.

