[REDACTED] A 7- to 14-day post-last dose follow-up visit and final follow-up visit approximately 28 days after the last dose will be performed for safety assessments [REDACTED]
[REDACTED]

[figure not shown]

Figure 3.1.1-1 Study Flow Diagram

ABPM = 24-hour ambulatory blood pressure (and heart rate) monitoring; AUC = area under the concentration-time curve; CGM = continuous glucose monitoring; Coh = cohort; [REDACTED]
 MMTT = mixed-meal tolerance test; n = number of subjects; V = visit

Assessments detailed in the schematics illustrate that those assessments will occur at that particular visit (unless specified otherwise), but they will not necessarily occur on the same day.

There is also a post-last dose visit 7 to 14 days after the last dose (Visit 10 for Cohort 1 and Visit 8 for Cohort 2), and there is a final follow-up visit (Visit 11 for Cohort 1 and Visit 9 for Cohort 2) approximately 28 days after the last dose for both cohorts.

The endpoints to be measured in this study are described in Section 2.

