PK for MEDI0382 ⁿ		X			X	X	X	X	X	X	X	X	X	X
ADA ^o			X						X					
[REDACTED]														
[REDACTED]														
Capillary blood ketone and beta hydroxybutyrate ^q		X			X							X		
Free fatty acids (predose)		X										X		
[REDACTED]														

Table 4.2.2-1 Schedule of Treatment Period Study Procedures: Cohort 1

Study Period	Inpatient		Inpatient or daily visits	Outpatient			Inpatient		Outpatient			Outpatient 7 to 14 Days Post Last Dose
	-2	-1		1	2-6	7	15	22	23	29	36	
Visit Number	V2			V3	V4	V5	V6	V7	V8	V9	V10	
[REDACTED]					■							
Fasting amino acids (predose)		X								X		
[REDACTED]		■								■		
Fasting uric acid		X								X		
[REDACTED]		■								■		
MMTT Type B - blood samples for glucose only ¹					X							
Collect urine for:												
Urinalysis (dipstick; predose as applicable)		X			X							X
Drug and alcohol screen	X											
MMTT Type C (no blood sampling) ^s		X										X
CGM device training	X	X	X									
CGM ^t	←	-----To be worn continuously throughout until Day 50-----→										
CGM sensor application/change ^u	X				X			X			X	
Glucometer and diary provision ^v	←	-----Subjects will be expected to check capillary blood glucose levels if they are unwell or have symptoms of hypoglycaemia-----→										
AEs/SAEs	←	-----For the duration of the study-----→										
Concomitant medications	←	-----For the duration of the study-----→										

Table 4.2.2-1 Schedule of Treatment Period Study Procedures: Cohort 1

Study Period	Inpatient		Inpatient or daily visits		Outpatient		Inpatient		Outpatient		Inpatient		Outpatient	
	-2	-1	1	2-6	7	15	22	23	29	36	43	49	50	7 to 14 Days Post Last Dose
Study Day														
Visit Number	V2		V3	V4	V5	V6	V7	V8	V9	V10				

ADA = anti-drug antibody; AE = adverse event; APBM = ambulatory blood pressure monitoring; BP = blood pressure; CGM = continuous glucose monitoring; D = day; ECG = electrocardiogram; GLP-1 = glucagon-like peptide-1; HbA1c = glycated haemoglobin; IP = investigational product; min = minutes; MMTT = mixed-meal tolerance test; PD = pharmacodynamic(s); PK = pharmacokinetic(s); RR = respiration rate; SAE = serious adverse event; SC = subcutaneous; V = Visit.

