4.2.3 Follow-up Period

Table 4.2.3-1 shows all procedures to be conducted during the follow-up period.

Whenever vital signs, 12-lead ECGs, and blood draws are scheduled for the same nominal time, the assessments should occur in the following order: 12-lead ECG, vital signs, and then blood draws.

After the end of the follow-up period, subjects will return to the care of their own physicians according to local requirements and local standards.

Table 4.2.3-1 Schedule of Follow-up Procedures

Study Period	Follow-up Period
Visit Number	Final
Procedure/Study Day	28 days post last dose (\pm 3 days)
Targeted physical examination	X
Weight	X
ECG	X
Vital signs (BP, heart rate, body temperature, RR) ^a	X
ABPM (Cohort 1 only)	X
	
Serum chemistry panel	X
Fasting lipid profile	X
Calcitonin ^c	X
Haematology	X
Urinalysis	X
HbA1c	X
Pregnancy test	X
MEDI0382 ADA ^d	X
Assessment of AEs/SAEs	X
Concomitant medications	X

ABPM = ambulatory blood pressure monitoring; AE = adverse event; ADA = anti-drug antibody; BP = blood pressure; ECG = electrocardiogram; HbA1c = glycated haemoglobin; min = minute; RR = respiration rate; SAE = serious adverse event; ULN = upper limit of normal

- ^a Blood pressure should be measured once at heart level in the nondominant arm where possible, after the subject has rested in either a seated or supine position for at least 10 minutes.
- ^b Subjects should fast for > 10 hours the night before; in the morning, a baseline blood test for glucose and insulin should be taken alongside a baseline measurement of expired CO₂ just prior to administration of C¹³- octanoate in conjunction with a standardised solid meal. Subjects will be expected to consume the meal within less than 5 minutes. Blood sampling of glucose and insulin should be performed at t = 0

Table 4.2.3-1 Schedule of Follow-up Procedures

Study Period	Follow-up Period
Visit Number	Final
Procedure/Study Day	28 days post last dose (± 3 days)

(baseline), t = 30 min, t = 60 min, t = 120 min and t = 240 min (± 5 min) after taking the standardised meal. Concurrent sampling of expired CO₂ should occur as described in the detailed methods section.

^c Only to be repeated if the calcitonin level was > ULN in the sample taken at the end of dosing

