6.3 Study Timetable and End of Study

An individual subject will be considered to have completed the study if the subject was followed through the last protocol-specified visit/assessment, regardless of the number of doses of investigational product that was received.

Subjects will be considered not to have completed the study if consent was withdrawn or the subject was lost to follow-up (Sections 4.1.5 and 4.1.6).

The end of the study (“study completion”) is defined as the date of the last protocol-specified visit/assessment for the last subject in the study.

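### Protocol Section 5.4.1 ends adverse event collection at the 7-14 day visit, but the schedules and Sections 5.4.2, 5.5 and 6.3 run to the 28-day final visit; new non-serious events are most exposed

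*Protocol*

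**What the plan says.** **Section 5.4.1** collects AEs from admission to the clinical unit, through treatment, and through a follow-up period that it defines in brackets as "7 to 14 days after the last dose of investigational product; Visit 10 for Cohort 1", with Visit 8 as the Cohort 2 counterpart. SAE collection starts earlier, at consent, but has the same end: "including the follow-up period as described above".

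**Section 3.1.1** shows that Visits 10 and 8 are not the last visits. It describes a separate "final follow-up visit (Visit 11 for Cohort 1 and Visit 9 for Cohort 2) approximately 28 days after the last dose".

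**Section 4.2.3, Table 4.2.3-1**, the schedule of follow-up procedures, has one visit column: the final visit at 28 days after the last dose, plus or minus 3. "Assessment of AEs/SAEs" is marked there.

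**Section 4.2.2, Tables 4.2.2-1 and 4.2.2-2** carry an AE/SAE row reading "For the duration of the study". **Section 6.3** defines the end of the study as "the date of the last protocol-specified visit/assessment for the last subject in the study".

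**Section 5.4.2** says that AEs still unresolved at the subject's last study visit are followed further without eCRF recording, so it takes the last visit as the end of recording. **Section 5.5** requires every SAE to be reported and entered in the eCRF, and sets a 24-hour notification rule for any SAE in the course of the study.

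**SAP Section 3.6.1** counts as treatment-emergent any AE after first receipt of investigational product and gives no closing date.

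**The concern.** The phrase *follow-up period* has two ends in the current protocol. Section 5.4.1 closes it at the 7-14 day visit. Section 4.2.3 uses the same name for a period that ends at the 28-day visit. Section 5.4.1 is the section titled as the AE collection period, and it names visit numbers and tables, so a site could reasonably treat it as the controlling rule.

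Safety and tolerability in dosing and follow-up is a secondary objective for both cohorts (Section 2.2). If some sites stop recording new AEs at Visit 10 or Visit 8 and others continue to Visit 11 or Visit 9, AE counts come from observation periods of different length. The reader of the tables could not tell a subject with no late events from one whose late events were not collected. Even among sites that all follow Section 5.4.1, the window differs between subjects by up to 14 - 7 = 7 days.

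**Working it through.** The plan gives no figure of its own here, so there is none to reproduce. The check compares the passages and then counts days.

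**1. Where each passage ends collection or reporting**

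| Protocol location | Non-serious AEs | SAEs |
|---|---|---|
| Section 5.4.1 | 7-14 day visit | 7-14 day visit |
| Tables 4.2.2-1 and 4.2.2-2 | duration of study | duration of study |
| Table 4.2.3-1 | assessed at 28-day visit | assessed at 28-day visit |
| Section 5.4.2 | recording ends at last study visit | recording ends at last study visit |
| Section 5.5 | not covered | all SAEs in the course of the study |
| Section 6.3 (end of study) | last protocol-specified visit | last protocol-specified visit |

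Section 5.4.1 is the only one with the earlier end. Section 5.5 backs up SAEs but has no counterpart for new non-serious AEs.

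**2. Days outside Section 5.4.1**

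Inputs: the stop day is 7 or 14 (Section 5.4.1). The final visit is nominally day 28, with a window of 25 to 31 (Table 4.2.3-1).

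Share uncovered = (final visit day - stop day) / final visit day.

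| Final visit day | Stop at day 7 | Stop at day 14 |
|---|---|---|
| 25 | 18/25 = 72% | 11/25 = 44% |
| 28 (nominal) | 21/28 = 75% | 14/28 = 50% |
| 31 | 24/31 = 77% | 17/31 = 55% |

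The nominal result is 14 to 21 days, or 50-75% of follow-up after the last dose (44-77% across the visit window).

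**3. The same days against the whole period from first dose**

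With 49 days of treatment and a nominal 28 days of follow-up, the total is 49 + 28 = 77 days. The uncovered share is then 14/77 = 18% to 21/77 = 27%. The treatment period itself is fully covered under every passage.

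**4. Drug exposure at the cut-off**

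Section 3.2.1 gives a half-life of about 8 to 13 hours. Day 7 after the last dose is 7 x 24 = 168 hours, which is 168/13 = 12.9 to 168/8 = 21 half-lives. Little drug remains, so few exposure-driven events should first appear after that point.

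**5. Effect of aligning Section 5.4.1 with the final visit**

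The uncovered share falls to zero. The collected period after the last dose rises from 7-14 days to 28 (25-31 with the window).

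**The case against.** **SAEs are protected elsewhere.** A reader might infer from Section 5.4.1 that an SAE with onset on, say, day 20 after the last dose would be lost. The documents do not support that. Section 5.5 requires all SAEs to be reported and recorded, and Section 6.3 keeps the study open to the last protocol-specified visit. Appendix 5 (Section 10.5) likewise applies the potential Hy's Law criteria at any point in the study after the start of investigational product. This objection stands. What remains for SAEs is conflicting instructions, not an expected loss.

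**Section 5.4.1 gives no instruction to stop.** This is true of the wording; the end is read from a bracketed definition. But the definition names the visits and the SAE sentence refers back to it, so reading it as a cut-off is the natural interpretation.

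**The final-visit assessment could be meant only for events already open.** That would reconcile the table with Section 5.4.1, but Table 4.2.3-1 does not limit the assessment in that way.

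**The treatment schedules are weak evidence, because their columns end at Visit 10 and Visit 8.** This is partly fair. The AE/SAE rows nonetheless refer to the whole study, and the argument does not need them: Table 4.2.3-1 and Section 6.3 are enough.

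**The percentage sounds larger than it is.** This stands. 50-75% is a share of calendar days after the last dose. It is not a share of events or of total AE observation time, and the upper end needs the early visit to fall on day 7.

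**The SAP loses nothing.** This also stands. With no closing date, SAP Section 3.6.1 excludes no late AE that has been recorded.

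**Conclusion.** The contradiction is in the current protocol text and should be resolved. Section 5.4.1 ends AE and SAE collection at the 7-14 day visit, against Table 4.2.3-1, the AE/SAE rows of Tables 4.2.2-1 and 4.2.2-2, and Sections 5.4.2, 5.5 and 6.3. Taken literally, it leaves 14 to 21 of 28 nominal post-dose days outside collection, for up to 63 subjects.

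The consequence is modest. The exposed data are mainly new non-serious AEs after Visit 10 (Cohort 1) or Visit 8 (Cohort 2), captured or not according to which passage a site follows. The stated half-life suggests that few of these would be exposure-driven. The efficacy analyses are untouched.

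Two stronger readings should be avoided: that late SAEs will go unreported, and that up to three quarters of the safety data are at risk. Section 5.5 answers the first, and the day count from first dose (18-27%) answers the second.

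The size rests on a nominal final visit at day 28, an early visit between days 7 and 14, and a site applying Section 5.4.1 to the letter. The documents do not show how many sites would do so.

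**What to change.** Amend Protocol Section 5.4.1 so that collection of both AEs and SAEs runs through the final follow-up visit, 28 days (plus or minus 3) after the last dose: Visit 11 for Cohort 1 and Visit 9 for Cohort 2. The start dates stay as they are. This brings the section into line with Tables 4.2.2-1, 4.2.2-2 and 4.2.3-1 and with Sections 5.4.2, 5.5 and 6.3, none of which then needs to change.

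The cost is one amended definition. No visit or procedure is added, because the AE/SAE assessment is already scheduled at the final visit.

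Optionally, add a sentence to SAP Section 3.6.1 stating that treatment-emergent AEs are counted through the same visit. This makes the analysis window explicit but is not needed to prevent loss of recorded data.
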